2.1 Primary estimands

The primary clinical question of interest is: What is the proportion of RMS patients having developed a specific immune response after receiving a SARS-CoV-2 mRNA vaccine (initial vaccination or booster vaccine) either before or after starting ofatumumab treatment.

The justification for the primary estimand is that it will capture whether ofatumumab-treated patients will mount a specific T-cell response after receiving a SARS-CoV-2 mRNA vaccine assessed by enzyme-linked immunosorbent spot (ELISpot) assays from T-cells that were stimulated with SARS-CoV-2 peptide mix.

Patients will receive either their initial vaccination (1st and 2nd SARS-CoV-2 vaccines) or a booster vaccine before or after starting ofatumumab treatment. In both cases we want to assess if ofatumumab initiation negatively affects or prevents the immune response.

Since this is not a randomized trial, no randomization needs to be preserved and the ITT-principle and the associated estimands framework do not apply. However, this protocol will keep as close as appropriate to the terminology and the definitions established within that framework.

The primary estimand is described by the following attributes:

1. **Population:** Patients with relapsing MS (RMS) divided in two cohorts, each receiving a SARS-CoV-2 mRNA vaccine as part of clinical routine: (1) vaccination before start of ofatumumab treatment, (2) vaccination after having been on stable ofatumumab treatment for at least 4 weeks. The SARS-CoV-2 mRNA vaccine can be either the initial vaccination cycle (for patient that are exposed to the vaccine for the first time; cohort 1a and cohort 2a) or a booster vaccination (for patients that have already completed the initial vaccination cycle; cohort 1b and cohort 2b). Patients in cohort 1a or 2a who fail to receive

their second dose of vaccine for whatever reason will be included in the analysis as non-responders. Patients in cohort 1a and 2a who did receive their second dose of vaccine and patients in cohort 1b and 2b who received their booster shot and do not have a valid determination of specific T-cell response to SARS-CoV-2 for whatever reason will be excluded from the analysis of vaccine efficacy.

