***Booster vaccination is optional can be performed any time after vacc.2. If a booster vaccination is given, an additional unscheduled visit should be performed 1 month after the booster vaccination in order to assess the immune reaction. If this unscheduled visit would be within 2 weeks of the next scheduled visit, the next scheduled visit can be omitted. This only applies for the first and second booster, there won't be any additional visits for potential following boosters.

Cohort 1b and cohort 2b:

PEP: primary endpoint; Vacc.= vaccination with modRNA vaccine;

Vaccination as part of clinical routine and before the study; required number of vaccinations and interval depends on SmPC of respective modRNA vaccines or local regulations provided e.g. by German health authorities.

First booster vaccination as part of clinical routine according to SmPC of respective vaccine or local regulations, e.g. German health authorities. Additional boosters can be performed any time during the study.

* Screening can be performed any time after completion of the initial vaccination cycle (vacc.2). For cohort 2b, ofatumumab treatment has to be initiated at or after screening but at least 4 weeks before booster vaccination

** Ofatumumab initiation doses can be omitted if patient already receives ofatumumab at the time of screening

*** Additional booster vaccination is optional can be performed any time after the first booster. If a second booster vaccination is given, an unscheduled visit should be performed 1 month after the second booster vaccination in order to assess the immune reaction. If this unscheduled visit would be within 2 weeks of the next scheduled visit, the next scheduled visit can be omitted. This only applies for the second booster, there won't be any additional visits for potential following boosters.

The study consists of 2 periods: run-in period and study period.

The **run-in period** comprises the time from screening to vaccination, including the baseline visit (approx. one week before the first vaccination). Patient eligibility will be determined based on the screening and baseline assessments.

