4.1 Rationale for study design

A two-cohort, multicenter, open-label, prospective design has been selected to generate data in a timely manner in order to provide a guidance for physicians and patients on the timing of initial and booster SARS-CoV-2 vaccination and the start of ofatumumab treatment in RMS patients. The study will assess two main questions:

- a) Can patients mount an immune response towards SARS-CoV-2 modRNA vaccines (initial vaccination or booster) when starting ofatumumab treatment after vaccination?
- b) Can patients mount an immune response towards SARS-CoV-2 modRNA vaccines (initial vaccination or booster) when receiving the vaccination while on stable ofatumumab treatment (for at least 4 weeks after the first ofatumumab dosing)?

A non-randomized design has been chosen to enable feasible recruitment as the patient's wish as well as the physician's discretion have to be taken into consideration when deciding on the timing of the vaccine and start of ofatumumab treatment.

Rationale for study population

Initiation and maintenance of ofatumumab treatment in this study will be performed as per approved SmPC. No inclusion/ exclusion criteria regarding age or disease severity were implemented in this study in order to reflect the clinical routine of ofatumumab patients in Germany as closely as possible. Therefore, all patients eligible for ofatumumab treatment and a SARS-CoV-2 modRNA vaccine may be suitable for KYRIOS as long as all other inclusion/exclusion criteria are met. In order to assess whether ofatumumab patients can mount an immune response after vaccination, patients with previous known COVID-19 disease will be excluded from the study.

Rationale for chosen endpoints

Recent publications about the immune responses after vaccination with the new SARS-CoV-2 modRNA vaccines show that both, BNT162b2 (Pfizer/BioNTech) and mRNA-1273 (Moderna), not only induced an antibody-response against the SARS-CoV-2 spike protein but also functional CD4⁺ and CD8⁺ T-cell responses (Jackson, Anderson et al. 2020, Sahin, Muik et al. 2020).

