5.2 Exclusion criteria

Participants meeting any of the following criteria are not eligible for inclusion in this study.

1. History of known COVID-19 infection (assessed based on patient statement and/or medical history) or current COVID-19 symptoms.
2. Participants who previously received a BTK inhibitor or an antiCD20 therapy other than ofatumumab
3. Patients likely not being able or willing to complete the study.
4. Use of other investigational drugs within 5 half-lives of enrollment/initiation of study treatment (e.g. small molecules) or until the expected pharmacodynamic effect has returned to baseline (e.g. biologics), whichever is longer
5. Patients with any medical or psychological condition that, in the investigators opinion, renders the patient unable to understand the nature, scope, and possible consequences of the study
6. No person directly associated with the administration of the study is allowed to participate as a study subject
7. No family member of the investigational study staff is allowed to participate in this study
8. No previous vaccination with a non-modRNA SARS-CoV-2 vaccine.

6 Treatment

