** If medically indicated, ofatumumab treatment might be started at an additional visit (A1) before visit 2 but at the earliest two weeks after the last vaccination.

*** Assessments don't have to be performed on visit 2 if ofatumumab treatment has already been initiated at visit A1.

**** Patients are allowed to receive SARS-CoV-2 booster vaccines any time after vacc. 2 according to respective SmPCs or local regulations, as part of clinical routine and at the physician's discretion. If patients receive a booster vaccination, additional visit 2 (A2) should be performed 1 month (4 weeks) after the booster vaccination to collect a blood sample and assess immune response. If the next scheduled visit falls within two weeks of visit A2, the scheduled visit can be omitted. This only applies for the first and second booster. All potential following boosters should be documented but there won't be any additional visits afterwards.

¹ According to approved SmPC requirements

² Contact can be on site, virtual or via phone according to physician's choice.

³ Laboratory test includes a standard hematology set, B-cell count, detection and characterization of SARS-CoV-2 specific T cells and neutralizing antibodies; if no SARS-CoV-2 specific T-cells can be detected, HLA-haplotyping will be considered to exclude methodical reasons. Blood samples will be stored.

⁴ MS relapses within the last two years should be reported

Table 8-2 Assessment schedule cohort 1b

concomitant medication												
Local urine and pregnancy test ¹	X		X	X**								
Administration of study drug at site			X	X**								
Self-injection training ¹			X	X**								
Study drug dispensation			X	X**						X	X	
Contact after modRNA vaccination ²		X						X				
Documentation SARS-CoV-2 vaccination	X	X						X				
Telephone contact					X	X	X					
AE/SAE	X	X	X	X	X	X	X	X	X	X	X	

White color: timing of visits depends on vaccination date

Grey color: Timing of visits depends on start of ofatumumab treatment and timelines have to be adjusted if ofatumumab treatment is initiated at visit A1 instead of visit 1. Visit 2: 1 week after start of ofatumumab treatment, visit 3: two weeks after start of ofatumumab treatment and visit 4: 4 weeks after start of ofatumumab treatment. Remote visits should be used to ensure that the first ofatumumab doses are applied according to SmPC.

A = additional visit; vacc. = Vaccination with modRNA vaccine,

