8.1.1 Eligibility screening

At screening, patients will be asked about previous COVID-19 disease. If a patient has had COVID-19 disease before screening, the patient is not eligible to further participate in the study.

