5.3 Statistical models

5.3.1 Primary analysis

The primary parameter “T-cell response” is derived from the laboratory data. Patients who have either SARS-CoV-2 reactive INFg-secreting T-cells or SARS-CoV-2 reactive IL-2 secreting T-cells (or both) are classified as responders. The assessment “equivocal” is rated as reactive for this analysis, which is based on observations made during the validation of the assay. It was noticed that the positive control of the ELISpot assay repeatedly provoked lower signals than seen in healthy volunteers, which led to the conclusion that T-cells from MS patients in general show lower reactivity in this assay. Consequently, the cut-offs for “reactive”/“equivocal” and “not reactive” defined by the kit-manufacturer have to be adjusted to these circumstances and results that would be classified as “equivocal” for healthy patients can be considered as signal and hence as “reactive” for MS patients. The following table presents the derivation of T cell response:

		Reactivity to INFg SARS-CoV-2 (quantitative)			
Reactivity towards IL-2 SARS-CoV-2 (quantitative)		reactive	equivocal	Not reactive	Missing value
	reactive	response	response	response	response
	equivocal	response	response	response	response
	Not reactive	response	response	Non-response	Non-response
	Missing value	response	response	Non-response	m.v. (not included in denominator)

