5.3.2 Secondary analysis

A patient achieves seroconversion when the neutralizing SARS-CoV-2 antibodies have changed from negative at screening/baseline to positive at the respective Visit. If the neutralizing SARS-CoV-2 antibodies are already positive at baseline (e.g. in patients of cohorts b who received their initial COVID-19 vaccine before the study) seroconversion cannot be derived for the post-baseline visits. These cases are displayed in addition in the tables as "already seroconverted at baseline".

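### In vaccine-naive cohorts 1a and 2a, no planned analysis shows the primary T-cell response rate without patients whose baseline antibody or ELISpot result suggests unrecognised earlier infection

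*Protocol*

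**What the plan says.** **Eligibility.** Protocol section 3 (run-in period) states: "Patient eligibility will be determined based on the screening and baseline assessments". The criterion on prior infection is Protocol 5.2, number 1: "History of known COVID-19 infection (assessed based on patient statement and/or medical history) or current COVID-19 symptoms". Protocol 8.1.1 describes the procedure: "At screening, patients will be asked about previous COVID-19 disease". Protocol 4.1 gives the purpose. So that the study can assess whether patients mount a response after vaccination, "patients with previous known COVID-19 disease will be excluded from the study".

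**Baseline blood.** Footnote 3 to the assessment schedules in Protocol section 8 reads: "Laboratory test includes a standard hematology set, B-cell count, detection and characterization of SARS-CoV-2 specific T cells and neutralizing antibodies". SAP 2.1.3 lists a baseline visit relevant for efficacy in every subcohort.

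**Who is vaccine-naive.** Protocol 2.1 describes the initial vaccination cycle as "for patient that are exposed to the vaccine for the first time; cohort 1a and cohort 2a".

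**Use of the baseline result.** SAP 5.3.2 defines seroconversion as a change from negative to positive. "If the neutralizing SARS-CoV-2 antibodies are already positive at baseline", seroconversion cannot be derived and the case is shown separately. The primary rule in SAP 5.3.1 has no baseline condition: "Patients who have either SARS-CoV-2 reactive INFg-secreting T-cells or SARS-CoV-2 reactive IL-2 secreting T-cells (or both) are classified as responders". Equivocal results count as reactive.

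**The concern.** A patient or a medical record can report only an infection that someone noticed. In 1a and 2a, SARS-CoV-2 neutralizing antibodies or reactive T cells before the first dose point to earlier exposure. Such a patient may have reactive T cells at Month 1 whatever the vaccine added. Protocol 1.1 supplies the mechanism: it cites specific CD4+ responses in all COVID-19 patients of one study, and immunological memory eight months after infection.

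The trial asks whether ofatumumab impairs or prevents the response. Cohort 2a is the subcohort given a first vaccination while on ofatumumab, and 1a is its counterpart vaccinated before ofatumumab. If primed patients respond more often than naive ones, the error runs towards showing a response and could hide part of the effect the trial is looking for.

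**Working it through.** **1. Where could baseline status enter the primary analysis?**

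| Place | Baseline antibody or ELISpot used? |
|---|---|
| Exclusion criteria (Protocol 5.2) | No |
| Intercurrent events (Protocol 2.1, SAP 2.5.1) | No |
| Efficacy analysis set (SAP 2.2) | No |
| Exclusion rules (SAP 5.4) | No |
| Responder rule (SAP 5.3.1) | No |
| Supportive analyses (SAP 2.5.4) | Reactivity and stimulation index by visit, not linked to Month 1 response |
| Seroconversion (SAP 5.3.2) | Antibody only, through the definition |

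**2. The plan's own precision.** Protocol 12.8.1 and SAP 3 give half-widths of 20.1%, 19% and 17.5% at n = 20. Using 1.96 × √(p(1 − p)/20):
- p = 0.70: 20.08 points
- p = 0.75: 18.98 points
- p = 0.80: 17.53 points

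The stated figures are reproduced. The planned Clopper-Pearson intervals are slightly wider: half-widths are 21.2, 20.2 and 19.0 points for 14, 15 and 16 responders of 20.

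**3. Size of the shift.** Let n be the number analysed, k the number primed by infection, and r the response rate in naive patients. Assume that all k respond.

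Observed rate = [(n − k)r + k]/n = r + k(1 − r)/n, so the shift is k(1 − r)/n.

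The values of r are the plan's planning rates. The documents do not give k, so 1 to 3 is an assumption. Shifts in points at n = 20:

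| r | k = 1 | k = 2 | k = 3 |
|---|---|---|---|
| 70% | 1.5 | 3.0 | 4.5 |
| 75% | 1.25 | 2.5 | 3.75 |
| 80% | 1.0 | 2.0 | 3.0 |

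If primed patients respond at 90% instead of 100%, the shift is k(0.9 − r)/n. At r = 70% that is 1.0, 2.0 and 3.0 points.

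The subcohort sizes are not fixed in the documents. With an assumed n = 10, every entry in the table doubles, giving 2 to 9 points. With k = 0 the shift is zero.

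**4. What a restricted row would show.** Suppose 14 of 20 vaccine-naive patients respond and k of the responders were positive at baseline:

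| Set | Rate | Exact 95% CI |
|---|---|---|
| All | 14/20 = 70.0% | 45.7 to 88.1 |
| Without 1 | 13/19 = 68.4% | 43.4 to 87.4 |
| Without 2 | 12/18 = 66.7% | 41.0 to 86.7 |
| Without 3 | 11/17 = 64.7% | 38.3 to 85.8 |

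**The case against.** **Limiting the exclusion to known disease is a consistent design choice.** This stands. Protocol 4.1, 5.2 and 8.1.1 agree with one another. A reader might infer that section 3 promises a laboratory criterion which 5.2 then drops. The sentence in section 3 is general and makes no such promise, so there is no contradiction.

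**The SAP does not treat infection inconsistently.** A reader might infer that it recognises prior infection for seroconversion and overlooks it for T cells. The treatment in 5.3.2 follows from defining seroconversion as negative to positive, and its own example is the booster cohorts. What remains is that the primary rate has no counterpart.

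**Baseline T-cell data are reported.** This is true, but it does not close the gap. The tables by visit in SAP 2.5.4 never give a Month 1 responder rate without patients positive at baseline. Fold change is listed as an endpoint in SAP 1.2, but SAP 2.7.1 describes no analysis of it. The post-hoc adjustment in SAP 2.3 and 2.5.4 is triggered by baseline differences and does not name serostatus. If both cohorts were equally affected, nothing would trigger it.

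**Antibody alone is a weak marker.** This stands and shapes the fix. Protocol 1.1 says that some patients, especially with mild disease, do not seroconvert, and that T-cell responses were the better marker of earlier coronavirus infection. In 2a, patients are sampled at baseline after ofatumumab has begun, so the antibody result may miss more infections there than in 1a.

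**The study is descriptive, and the cohort rate pools subcohorts a and b.** This limits the consequence. However, Protocol 12.4.4 plans to analyse initial and booster vaccination separately, and the issue bears on the initial-vaccination results.

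**Conclusion.** The concern holds in a limited form. In 1a and 2a, the plan offers no view of the primary response rate free of patients already positive at baseline, although the samples that would identify them are part of the study. If primed patients respond more often than naive ones, the rates are biased upward. The shift is 1 to 4.5 points at n = 20 for r of 70% to 80%, assuming one to three primed patients who all respond. It is larger in a smaller subcohort and zero if there are none. It is well below the half-width of about 19 to 21 points, but the interval covers sampling error only and does not reflect it.

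Three stronger inferences are not supported:
- Infected patients do not count as responders automatically. They must be reactive or equivocal at Month 1.
- The rates in 1a and 2a do not both describe vaccination on ofatumumab. Cohort 1a is vaccinated before it starts.
- The documents do not show that any such patient was enrolled, so the bias is possible and not demonstrated.

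**What to change.** In SAP 2.5.4, pre-specify that the Month 1 T-cell response rate is shown separately for 1a and for 2a, with exact 95% CI, for:
1. all patients;
2. patients negative for neutralizing antibodies at baseline;
3. patients negative at baseline for both neutralizing antibodies and SARS-CoV-2 ELISpot (IFNg and IL-2).

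Code the baseline ELISpot as in SAP 5.3.1, with equivocal counted as reactive, and give the number of patients with missing baseline results. State that conclusions about a first vaccine response in 1a and 2a will be checked against rows 2 and 3.

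Leave the primary analysis unchanged. Do not apply the restriction to 1b and 2b, where positivity at baseline is expected from earlier vaccination.

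The cost is two flags from baseline data that the plan already collects and a few table rows, with no new sample. The restricted rows will have slightly fewer patients and wider intervals. Some baseline ELISpot reactivity may not reflect SARS-CoV-2 infection, and antibody alone may miss infections, so both rows 2 and 3 are needed.

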4.1 Rationale for study design

A two-cohort, multicenter, open-label, prospective design has been selected to generate data in a timely manner in order to provide a guidance for physicians and patients on the timing of initial and booster SARS-CoV-2 vaccination and the start of ofatumumab treatment in RMS patients. The study will assess two main questions:

- a) Can patients mount an immune response towards SARS-CoV-2 modRNA vaccines (initial vaccination or booster) when starting ofatumumab treatment after vaccination?
- b) Can patients mount an immune response towards SARS-CoV-2 modRNA vaccines (initial vaccination or booster) when receiving the vaccination while on stable ofatumumab treatment (for at least 4 weeks after the first ofatumumab dosing)?

A non-randomized design has been chosen to enable feasible recruitment as the patient's wish as well as the physician's discretion have to be taken into consideration when deciding on the timing of the vaccine and start of ofatumumab treatment.

Rationale for study population

Initiation and maintenance of ofatumumab treatment in this study will be performed as per approved SmPC. No inclusion/ exclusion criteria regarding age or disease severity were implemented in this study in order to reflect the clinical routine of ofatumumab patients in Germany as closely as possible. Therefore, all patients eligible for ofatumumab treatment and a SARS-CoV-2 modRNA vaccine may be suitable for KYRIOS as long as all other inclusion/exclusion criteria are met. In order to assess whether ofatumumab patients can mount an immune response after vaccination, patients with previous known COVID-19 disease will be excluded from the study.

Rationale for chosen endpoints

Recent publications about the immune responses after vaccination with the new SARS-CoV-2 modRNA vaccines show that both, BNT162b2 (Pfizer/BioNTech) and mRNA-1273 (Moderna), not only induced an antibody-response against the SARS-CoV-2 spike protein but also functional CD4⁺ and CD8⁺ T-cell responses (Jackson, Anderson et al. 2020, Sahin, Muik et al. 2020).

Especially in the context of ofatumumab treatment and the imminent B-cell depletion, the activation of CD4⁺ and CD8⁺ T-cells plays a very important role for the development of vaccine-induced immunity. The primary endpoint in this study was therefore chosen in analogy to the recently completed trials and in-depth analyses of the modRNA vaccines BNT162b2 (ClinicalTrials.gov Identifier: NCT04368728, (Sahin, Muik et al. 2020, Walsh, Frenck et al. 2020)) and mRNA-1273 (ClinicalTrials.gov Identifier: NCT04283461, (Jackson, Anderson et al. 2020)).

4.2 Rationale for dose/regimen and duration of treatment

Ofatumumab

All patients in this study will be treated with ofatumumab (20 mg s.c.) according to approved SmPC to be as close to the clinical routine as possible. Cohort 1 will start ofatumumab treatment four weeks after the second SARS-CoV-2 modRNA vaccination (1a) or four weeks after SARS-CoV-2 booster vaccination (1b), cohort 2 will already have been on stable ofatumumab treatment at the start of the study or will start ofatumumab treatment at least 4 weeks before the first vaccination (2a) or before booster vaccination (2b) and will remain on stable treatment until completion of the study.

Vaccination

In this study, patients will receive a modRNA vaccine at the discretion of the treating physician as part of the clinical routine and according to the respective SmPC or local regulations provided e.g. by German health authorities. If suggested by local regulations, patients are allowed to receive additional SARS-CoV-2 vaccines (as booster or yearly refresher) as per physician's discretion.

